CRUK	Cancer Research United Kingdom
GP	General Practitioner
HADS	Hospital Anxiety and Depression Scale
NIHR	National Institute for Health Research
ORION	Outcome Registry Intervention and Operation Network
PI	Principal Investigator
PM	Practice Manager
SSM	Skin self-monitoring
RCT	Randomised Controlled Trial
RISP	Research Information Sheet for Practices
SMS	Short messaging service

2. Protocol Synopsis

Title	Skin-Self Monitoring for primary care patients at higher risk of melanoma: a phase II RCT
Short Title	MelaTools SSM Trial
Funding	NIHR- Clinician Scientist Award
Chief Investigator	[name]
Research Purpose	To test a novel skin self-monitoring (SSM) intervention in general practice aimed at promoting timely consulting by people at 'above-population' risk of melanoma
Aims	 To evaluate SSM App use compared with standard information on skin change appraisal and help-seeking among patients at 'above-population' risk of melanoma; To optimise the intervention, to establish its acceptability and to collect all the relevant data to inform a subsequent phase III trial.
Study Design	Phase II, multi-site RCT
Study Setting	Patients with an 'above-population' risk of melanoma will be recruited from general practices in CRN Eastern.
Sample size & recruitment	Based on our recent MelaTools Q study, we anticipate that we will need to approach approximately 2,000 people to have 1,600 completed questionnaires; 400 people (25%) will be at higher risk and eligible, and 50% of these will need to attend the trial consultation in order to reach our target of 200 participants.
Inclusion Criteria	 ≥18 years of age ≤ 75 years of age Ability to read and write for informed consent and smartphone use
Exclusion Criteria	 Severe psychiatric or cognitive disorder Physical disorder severe enough to inhibit the use of a smartphone No smartphone
Randomisation	Patients will be randomised 1:1 to either control or intervention group.
Intervention	All participants in both groups will have a standardised consultation about prevention of skin cancer with the research nurse. Those in the intervention group will also be provided with a SSM App and standardised tuition on use.
Duration of individual's participation	Study participation will last no longer than 12 months; patient-reported outcomes will be collected at baseline, 6 months and 12 months post-consultation.
Process and Outcome Measures Study duration	 We will examine processes relating to use of the SSM App, including: Patient outcomes: patient interval (time from first noticing skin change to consultation); sun protection habits, skin self-examination, melanoma worry and perceived melanoma risk, self-efficacy for consulting without delay; anxiety, depression and quality of life; Clinical outcomes: melanoma (and other skin cancer) diagnosis; actions during consultations: diagnosis, referral, excision, monitor; Practice outcomes: consultation rates; Trial processes: feasibility and acceptability; Incidence of melanoma (and other skin cancer) diagnosis across participating practices and their regions during the trial and after 5 years. It is anticipated that the study will be completed by March 2018.

3. Funding

[name] received a NIHR Clinical Scientist award (NIHR-CS-012-030) in June 2012 to fund the MelaTools programme. This is the final study in this programme.

4. Co-Investigators and Collaborators

[figure not shown]
Principal			
Investigator	University	Country	Role
[name]	University of Cambridge	England	Management and oversight of the study
Co-Investigators [name]	University of Melbourne	Australia	Advising on the design, implementation and analysis of the study
[name]	Cambridge University Hospitals NHS Foundation Trust	England	Advising on the design, implementation and analysis of the study
[name]	Cambridge University Hospitals NHS Foundation Trust	England	Advising on the design, implementation and analysis of the study
[name]	University of Aberdeen	Scotland	Advising on the design, implementation and analysis of the study
[name]	University of Cambridge	England	Co-ordinating and conducting the research

Collaborators			
[name]	University of Cambridge	England	Advising on the design, implementation and analysis of the study
Or [name]	University of Cambridge	England	Statistical support
[name]	University of Cambridge	England	Liaison with Cambridge Clinical Trials Unit, expertise in trial management

6.1 Purpose

This phase II pilot randomised controlled trial (RCT) tests a novel intervention of the use of a Skin Self-Monitoring (SSM) smartphone application ('App'), and self-monitoring monthly reminders, to promote timely consulting for skin changes/pigmented skin lesions by people at above-population risk of melanoma.

6.2 Aims

- **1.** To assess the effect of using a SSM App compared with standard information on the patient interval among patients at above-population risk of melanoma;
- **2.** To obtain preliminary estimates of effect across a range of outcome measures to inform selection of the primary outcome for a definitive phase III trial.

6.3 Hypotheses

- **1.** The MelaTools SSM Trial intervention will increase the number of consultations for pigmented skin lesions in people at above-population risk of melanoma;
- 2. The MelaTools SSM Trial intervention will be acceptable and will reduce the patient interval (including symptom appraisal and help-seeking intervals) in people at above-population risk of melanoma;
- **3.** The MelaTools SSM Trial intervention will not cause significant distress or worry in people at above population risk of melanoma.

7. Background

7.1 Cutaneous malignant melanoma

Melanoma is the leading cause of skin cancer deaths in the UK with 2,148 in 2012 (1). Melanoma incidence has quadrupled over the last 30 years and is continuing to rise (2). Although it is more common with increasing age, it is disproportionately high in younger people (3, 4). Risk factors include fair skin, family history of melanoma, multiple naevi, and sun damage. Melanoma is associated with significant morbidity, and the thickness of the lesion at diagnosis is the most important prognostic factor: stage 1 disease has 5-year survival rates of over 95%, compared to less than 40% for stage 4 disease (5). The UK has lower 1- and 5-year melanoma survival rates than comparable countries in Europe (6). Diagnostic delays are thought to contribute to this, and there is evidence of avoidable delay; the UK policy focus on identifying and reducing these delays has aimed to save 5-10,000 lives a year across all cancers (7). Although findings from the SCREEN project in Germany suggests that population screening may have a substantial impact on melanoma incidence and 5 year mortality (8), routine screening of the general population using a total body skin examination is not currently recommended in the UK. Therefore a focus on secondary prevention through early, timely detection and prompt treatment could make an important contribution to melanoma outcomes.

7.2 Patient Interval

Current literature demonstrates that patient pathways to presentation and management in primary care are key determinants in cancer outcomes (9, 10). When compared with people diagnosed with other cancers, those diagnosed with melanoma have the second longest median time between first noticing a symptom and presenting to primary care (patient interval) (11). There is a need to optimise this time period by assessing the factors which influence the patient interval, namely symptom appraisal and help-seeking intervals (12), for skin changes suspicious of melanoma. Our team's studies have highlighted the need to provide patients with clear information on the

symptoms of melanoma and guidance on monitoring skin changes (13, 14). Policy and third sector approaches have aimed to raise symptom awareness and promote timely help-seeking. More targeted approaches could prioritise education for those patients at higher risk, and promote tools and new technologies that focus on detecting early signs of melanoma.

7.3 Smartphone Applications

Smartphones have been termed 'the new clinical tools in oncology' (15). Most (>75%) of the UK population now own a smartphone, and they have quickly changed from being devices for communication to include specialized applications ('Apps') that are intimately involved in many aspects of daily life. Many Apps now focus on health issues, presenting new opportunities for risk assessment, symptom appraisal, monitoring symptoms and signs over time, and cues to seek professional advice. The use of such Apps for detecting skin changes could potentially assist in earlier diagnosis of melanoma, in prompting users to monitor their pigmented skin lesions over time, and in suggesting professional, timely review of any suspicious moles detected. Before healthcare providers can recommend an App to their patients they need to be confident that the App will not cause any harm, will be user-friendly, and will aid recognition of the target disease or behaviour (16).

7.4 Skin Self-Monitoring (SSM)

Up to 75% of melanomas are detected by people or their family/friends (rather than health care professionals) (17). To maximise the effectiveness of SSM the person performing the examination should be able to identify skin changes and features of skin lesions which could indicate melanoma, yet recent studies have demonstrated that suspicious signs of early skin changes may not be widely known (18,14). Educating patients and the public is possible: newly diagnosed Italian melanoma patients who performed self-skin examination were found to have thinner tumours (19), and Australian melanoma patients were found to adhere to medical advice on skin self-examination during follow-up care (20). A recent Scottish study has demonstrated melanoma patients are prepared to use digital technology to support them in conducting SSM during follow-up (21). We therefore set out to explore using mobile technology for SSM among people at higher risk of melanoma in the primary care setting to encourage timely consultation for possible melanoma.

7.5 Phase I studies

Two recent studies have provided data to inform the Phase II RCT.

7.5.1 MelaTools Q Study

Defining higher-risk populations using risk prediction models may help targeted screening and early detection approaches. We recruited participants from the waiting rooms of 22 general practices covering a total population of >240,000 in three UK regions: Eastern England, Northeast Scotland, and North Wales. Participants completed an electronic questionnaire incorporating the Williams melanoma risk model (22) using tablet computers. 7,742/9,004 approached people completed the electronic questionnaire (86%). The mean melanoma risk score for the 7,566 eligible participants was 17.15 (SD 8.51), with small regional differences, mainly due to greater freckling and childhood sunburn among Scottish and Welsh participants. We concluded that collecting data on the melanoma risk profile of the general population in UK primary care is both feasible and acceptable, and provides opportunities for new methods of real-time risk assessment and risk stratified cancer interventions (23).

7.5.2 MelaTools-Apps Study

This recent study aimed to understand community user views on the usefulness and usability of Apps for SSM. Participants were recruited through general practice waiting rooms via poster advertisements, and stratified into two melanoma risk groups using the MelaTools Q risk assessment questionnaire. Those at above-population risk were invited to participate in an introductory workshop, a diary to complete over 3 months, and then a face to face interview. Each participant

tested one or more of the following Apps: FotoSkin, MoleMonitor, SkinVision, UMSkinCheck and MySkinPal. All these Apps encourage photographing skin changes, and suggest that the user compares these images over time. Other options include completion of a full body check with prompts to monitor certain body areas offered, and skin cancer awareness information. The initial results from this study have provided insight into the usability of these Apps, and guided decision-making on which App to be used in this phase II trial.

8. Research Methods

8.1 Study Design and Outcomes

We applied the well-established MRC methodological framework for the design and evaluation of complex interventions to provide preliminary data to inform the design of this phase II RCT (24, 25). As this is a feasibility trial there will be two primary outcomes:

Primary Outcome/s

- a. Consultation rates for any skin changes/pigmented skin lesions presented to their GP/practice nurse during the 12 months following the trial consultation compared with the 12 months prior to the trial and;
- b. The patient interval (PI) for all skin changes/pigmented skin lesions presented to their GP/practice nurse during the 12 months following the trial consultation.

Secondary Outcomes will include:

- a. Patient-Reported Outcomes, including: sun protection habits, skin self-examination, melanoma worry and perceived melanoma risk, self-efficacy for consulting without delay; anxiety, depression and quality of life;
- **b.** Trial feasibility and acceptability, including: data on patient recruitment, attrition, and response rates to outcome measures to inform decisions about a future phase III trial;
- c. Melanoma incidence across participating practices, to contextualise trial findings and after 5 years.

8.2 Study setting and practice recruitment

Participants will be recruited via general practices in the East of England. GP practice recruitment will be supported by CRN:Eastern who will approach practices in the designated geographical regions, favouring Research Site Initiative (RSI) practices. Recruitment will focus on RSI practices because these practices have an ongoing commitment to research and, generally, have allocated research nurse time. In practices which do not have funded research nurse time, a research nurse from the CRN will be funded to support the study.

8.3 Intervention

8.3.1. Development of standardised consultation and intervention

A detailed consultation script and training module developed by the research team will guide the research nurses conducting the consultation and delivering the intervention. The instructions for using the SSM App have been piloted in the MelaTools-Apps study.

8.4 Recruitment Approach & Participant eligibility/exclusion criteria

The recruitment approach developed for the MelaTools Q Study was very successful (7,742/9,004 approached people completed the electronic questionnaire- 86%); the same recruitment strategy will be used in this trial. People aged between 18-75, attending the general practice as a patient or companion, will be invited to take part. Researchers will recruit participants opportunistically in the reception area at different times of the day and different days of the week, in order to ensure a broad range of ages, gender, and educational level are approached. People will not be invited to take part if they exhibit any of the exclusion criteria:

- Severe psychiatric or cognitive disorder;
- Inability to read English to a reasonable standard;
- Physical disorder severe enough to inhibit the use of a smartphone.

Those willing to take part will be invited to complete an electronic questionnaire using tablet computers. The gender and reason for not wishing to participate will be recorded for each person choosing not to take part.

The electronic questionnaire's MelaTools Q risk assessment tool will be preceded by a consent form. Real-time risk assessment will then stratify respondents into 'population risk' (majority) and 'above-population risk' (minority) groups. People at 'population risk' will be thanked, and given the Cancer Research UK leaflets on risk factors of melanoma and melanoma prevention advice. People at 'above-population' risk will be invited to participate in the trial, and given the Participant Information Sheet and an appointment time within 14 days for the SSM Trial consultation. This will be confirmed by email or post as the potential participant prefers.

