8.5 Randomisation

At the trial consultation, and once fully consented, participants will be randomised 1:1 to either the control arm (standard information) or to the intervention arm (standard information and SSM App). A block randomisation method, using computer-generated, randomly permuted blocks of size 2, 4, and 6, established by the trial statistician, will be applied. Sets of numbered, sealed envelopes will be prepared, with the order of the sequences verified on completion of the trial.

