8.7.2 Primary care

The GP practice managers will run a monthly search of their general practice's electronic medical records to identify all study participant consultations with GPs and practice nurses. If a consultation concerned a skin change/pigmented skin lesion, a Skin Symptom Questionnaire will be sent to the participant, with a letter explaining why they are receiving this additional questionnaire and a FREEPOST envelope. They will be mailed one reminder after 2 weeks if the questionnaire is not returned.

After trial completion, a final audit of the GP electronic medical records will be run to identify all skin consultations for the 12 months during the trial as well as the previous 12 months.

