5. TRIAL POPULATION 155 Screening data 156 157 We will report the number of patients assessed for eligibility before recruitment. Eligibility 158 Inclusion criteria 159 160 People aged between 18 and 75 years who own a smartphone (Apple or Android), and, on completion of 161 the Melatools-Q risk assessment tool (Williams et al, 2011), are found to be at increased risk of 162 melanoma. Participants are able to read and write English and to give informed consent. Exclusion criteria 163 Previous diagnosis of melanoma, severe psychiatric or cognitive disorders, or a physical disorder severe 164 165 enough to inhibit the use of a smartphone. Recruitment 166 167 We will report a CONSORT patient flow diagram, including the number of patients 168 assessed for eligibility at screening eligible at screening 169 ineligible at screening * 170 171 eligible and randomised eligible but not randomised * 172 received the randomised allocation 173 174 did not receive the randomised allocation * lost to follow-up * 175 discontinued the intervention * 176 177 randomised and included in the primary analysis randomised and excluded from the primary analysis * 178 179 * reasons will be provided 180 Specifically, for this analysis, we will report in full 181 response rates to each of the PRO surveys (baseline, 6 and 12 months) 182 response rates to the patient interval surveys 183 We will also report 184 item non-response to each survey item among responders 185 Timings for any withdrawals

Baseline characteristics

186

187 We will provide summary statistics on baseline characteristics overall and by arm.

We will describe the median (IQR) consultation rate in the year before randomisation, as well as the median (IQR) age at randomisation and the proportion female. We will further describe the mean (standard deviation) of each of the 9 scale secondary outcome measure, and the baseline distribution of the additional secondary measures which do not form part of a scale.

193 **6. ANALYSIS**

194 Outcome definitions

- 195 Primary outcomes
- 196 Consultation rate
- 197 The number of consultations for skin changes/pigmented skin lesions per person in the 12 months
- 198 following randomisation.
- 199 This will be collected monthly by a search of general practice records. Practices with zero recorded
- 200 consultations at the end of the trial will be higher priority for visits to check for failure to report data.

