- inform analysis choice in the phase III trial. For this analysis, we will use Poisson regression.

- 302 Missing data
- There should not be missing data in this outcome as we assume zero consultation rates are true zeros.
- 304 Statistical analysis
- 305 First, we will describe the pre- and post- intervention consultation rates overall and by group,
- 306 summarising using median (IQR) and mean (SD). We will not perform a statistical test, but this will be
- 307 useful information for sample size calculations for the phase III trial.
- The main analysis will be an unadjusted Poisson regression.

Consultation rate, post =
$$\exp(\beta_0 + \beta_1 \times (Intervention))$$

- 309 In Stata code
- 310 glm consult_post i.treat, family(poisson)
- 311 A sensitivity analysis will adjust for demographic information and include a random effect for general
- 312 practice.

Consultation rate, post

=
$$\exp(\beta_0 + \beta_1 \times (Intervention) + \beta_2 \times (Female) + \beta_3 \times (Age in years) + b_1)$$

- Where $b_1 \sim N(0, \sigma_1^2)$ is a random effect to capture GP effects.
- 314 In Stata code
- meglm consult_post i.treat i.female c.age, family(poisson) || practice:
- 316 We will explore the impact of allowing for non-linear associations with age, by introducing a
- 317 changepoint at 65 years.
- 318 Analysis of patient interval among patients who have had a consultation
- 319 Data quality checks

- Plot a boxplot of all the patient intervals
- 321 Plot a histogram of all the patient intervals
- We know from Lyratzopoulos et al (2015) that the quartiles of the patient interval for a different sample of patients with melanoma were Min: 0, Q1: 0, Q2: 21, Q3: 69, pct90:
- 324 234 days. We will have concerns about either data quality or generalisability if more
- 325 than 25% of patients have a patient interval of 80+ days.
- 326 Analysis planning
- 327 The protocol specifies standard linear regression, and includes flexibility on the particular analysis in
- 328 case data are highly skewed.
- 329 We will use linear regression to analyse these data. We will also tabulate consultations by trial arm and
- whether the patient interval was more (or less) than 21 days.

- 331 Missing data
- We expect missing data in this outcome, because it is based on a survey of patients and not all patients
- will respond.
- In the first instance, we will compare rates of missing data between the intervention and control groups.

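### Companions can be randomised without being registered at a participating practice, so their unseen skin consultations count as true zeros and understate the absolute consultation rates

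*Protocol*

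**What the plan says.** **Who can enter.** Protocol section 8.4: "People aged between 18-75, attending the general practice as a patient or companion, will be invited to take part". The synopsis lists age and "Ability to read and write for informed consent and smartphone use". SAP section 5 starts from "People aged between 18 and 75 years who own a smartphone (Apple or Android), and, on completion of" the risk tool, are at raised risk, and adds literacy and consent. The exclusions concern psychiatric, cognitive or physical disorder, reading English, lack of a smartphone and (SAP only) previous melanoma. None of these lists mentions where the person is registered. Section 8.5 continues: "At the trial consultation, and once fully consented, participants will be randomised 1:1". No registration check is described at screening, consent or randomisation.

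**What is counted.** Section 8.1 defines the first primary outcome as skin consultations "presented to their GP/practice nurse during the 12 months following the trial consultation compared with the 12 months prior to the trial".

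**Where it is found.** Under section 8.7.2 practice managers "run a monthly search of their general practice's electronic medical records to identify all study participant consultations with GPs and practice nurses". A final audit of GP records covers the trial year and the year before, and section 8.8.2 describes the source in the same way. SAP section 6 uses a monthly search of general practice records, with checking visits hoped for at the 12 trial practices.

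**How it is analysed.** Protocol section 9.5 and SAP section 4 include everyone randomised. SAP section 6 fits an unadjusted Poisson regression to the post-randomisation count and says of missing data: "There should not be missing data in this outcome as we assume zero consultation rates are true zeros".

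**The concern.** The eligibility rule and the data source do not cover the same people. A companion registered at another practice can be eligible, consent and be randomised. Their skin consultations will normally be recorded at a practice that nobody searches. For that person the zero, both before and after randomisation, is an unobserved value, yet the SAP treats it as observed.

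The planned checks would not find it. They look for practices with no consultations, practices with unusual rates, and patients with four or more consultations. One person with a zero looks like any other.

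The same record search triggers the Skin Symptom Questionnaire, so these people also supply no patient interval. They are not counted as non-responders, because no questionnaire is sent.

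At stake are mainly the absolute consultation rates, which the SAP wants for phase III sample size calculations, and to a lesser degree precision.

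**Working it through.** **The plan's own figure.** Section 9.4 expects 1,600 completed questionnaires, 25% at raised risk and 50% attending: 1,600 × 0.25 × 0.50 = 200. The target reproduces. With 1:1 allocation this is 100 per arm.

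**Assumed input.** Let c be the share of randomised people not registered at a searched practice. The documents give neither a companion share nor c, so a range is used: 1%, 5%, 10%, 20%.

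**Formulas.**
- Observed rate = (1 − c) × true rate, in each arm and in each 12-month period.
- Rate ratio multiplier = (1 − c_int)/(1 − c_ctrl), which is 1 when the shares are equal. Randomisation makes them equal in expectation.
- SE(log rate ratio) = √(1/m0 + 1/m1), with m = 100 × observed rate per arm. Relative to observing all 200, this rises by 1/√(1 − c).
- 95% range of the rate ratio shift from chance imbalance in c alone = exp(1.96 × √((c/(1 − c)) × 2/100)).
- Phase III size inflation, if phase III observes all its participants = 1/(1 − c).
- Number to approach for 200 registered participants = 2,000/(1 − c), if the share is the same at every recruitment step.

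| c (assumed) | Observable of 200 | Rates understated by | SE factor | Chance shift, up to | Phase III factor | Approach |
|---|---|---|---|---|---|---|
| 1% | 198 | 1% | 1.005 | 1.03 | 1.01 | 2,021 |
| 5% | 190 | 5% | 1.026 | 1.07 | 1.05 | 2,106 |
| 10% | 180 | 10% | 1.054 | 1.10 | 1.11 | 2,223 |
| 20% | 160 | 20% | 1.118 | 1.15 | 1.25 | 2,500 |

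**Chance shift against ordinary sampling error.** Assume, for illustration only, a true control rate of 0.2 per year and a rate ratio of 1.5. SE(log rate ratio) is then 0.296, 0.304 and 0.323 at c = 5%, 10% and 20%. The 95% factors are exp(1.96 × SE) = 1.79, 1.82 and 1.88. At c = 20%, adding the imbalance variance 0.2/0.8 × 2/100 = 0.005 gives √(0.323² + 0.005) = 0.330 and a factor of 1.91. The imbalance therefore adds about 2.4% to the SE at c = 20% and less at smaller shares.

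**Over-dispersion.** False zeros make the variance-to-mean ratio 1 + c × rate. At c = 20% and an intervention rate of 0.3 this is 1.06, a small effect.

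**What restriction changes.** Dropping unregistered people from the consultation analysis leaves m0 and m1 unchanged, so it does not recover the lost precision. It corrects the absolute rates and removes the chance imbalance. Precision returns only if 200 registered people are recruited.

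**The case against.** The documents can be read as presuming registration. The synopsis speaks of patients, the outcome refers to the participant's own GP, and the incidence section of the SAP mentions patients registered at these practices. Consent pages are not in the text available, and registration wording there cannot be ruled out. But a presumption is not a criterion, and section 8.4 expressly invites companions.

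The final audit is not expressly confined to the recruiting practice, and the trial must know each participant's GP to send the HADS letter in section 8.7.1. That shows outside records might be reachable. No step obtains them, no outside practice is named, and the SAP's checks concern the 12 trial practices.

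Other points stand and limit the concern:
- The share is unknown. Some companions will be registered at the same practice, and at 1% the effect is trivial.
- A reader might infer that the rate ratio is biased. It is not in expectation, because registration status is fixed before randomisation.
- A reader might infer that chance imbalance threatens the comparison. It is small beside ordinary sampling error, and the SAP says the trial is not powered for its primary outcome.
- A reader might infer that patient interval is contaminated. It is defined only among people with a consultation, so it loses observations and receives no false values.
- Oversizing of phase III follows only if phase III observes all its participants, for instance by restricting to registered people. If it recruits and searches in the same way, the diluted rate is the right planning value.

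**Conclusion.** The gap is real and of moderate importance. Followed as written, the plan can randomise people whose consultations it cannot see, and it codes them as zero. The absolute pre- and post-trial rates are then too low by the unregistered share: 1% to 20% over the assumed range, with a rise in the SE of the log rate ratio of about 0.5% to 12%. These sizes rest on that assumed range and on unregistered people having the same true rates as the others.

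The documents do not support a claim that the between-arm comparison is systematically wrong. The defect lies mainly in the descriptive quantities meant for phase III planning and in the statement that the outcome has no missing data.

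**What to change.** 1. Add registration at a participating practice to the eligibility criteria in protocol section 8.4 and SAP section 5, and check it before randomisation.
2. For people already randomised, establish registration status as at randomisation and report the number not registered by arm.
3. Treat those people's consultation count as missing, not zero. State openly that the consultation analysis is then restricted on a pre-randomisation characteristic and so departs from the all-randomised population. Keep the all-randomised analysis as a sensitivity analysis.
4. Keep these people in the questionnaire outcomes.
5. Limit the true-zeros statement in SAP section 6 to participants registered at a searched practice.

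The cost is one screening question, one eligibility line, a short SAP change and a status check for those already enrolled. Some companions are lost from recruitment: under the assumed shares, about 2,021 to 2,500 people would be approached instead of 2,000.
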